#### Step 3. Obtain Informed Consent

Patients who express interest in participating will be informed in greater detail about the study and receive screening for eligibility criteria by the PI psychiatrist or the research assistant. The patients will learn about general requirements for participation (e.g., need for follow-up, participation in assessments, etc.) as well as risks associated with nicotine toxicity, nicotine withdrawal, blood draw, and pharmacotherapy. If still interested and eligible, the patients will then be asked to provide written informed consent to participate, on a form approved by the Washington University School of Medicine Institutional Review Board. Study candidates will read the informed consent document and be given an opportunity to ask any questions regarding study participation. They will also complete the HIPAA form and the consent form. A

follow up contact can be scheduled if potential participants would like to have more time to consider participation. Participants will receive a signed copy of the consent document.

## ***E2 Schedule of Measurements***

Participants will receive a baseline assessment of smoking history and withdrawal symptoms, provide a breath sample for alveolar CO level, provide blood sample for assessments of nicotine metabolism and genetic markers, receive smoking cessation counseling, and be randomized to one of two groups (transdermal nicotine replacement therapy and counseling vs placebo and counseling). These evaluations will be conducted by the Principal Investigator [name] or a research assistant. The baseline assessment will take approximately 90 minutes. Participants will be asked to also participate in 8 follow up visits, two in person at 3 months (if biochemical verification is needed) and 6 months (if biochemical verification is needed) and the rest by phone at the last pre-quit, quit date, 1 week, 2 weeks, 4 weeks, 3 months (if biochemical verification is not needed), 6 months (if biochemical verification is not needed) and 1 year after the quit date.

	office	office	phone	phone	phone	phone	phone	office/phone	office/phone	phone
Reimbursement	\$25	\$25/\$40	N/A	N/A	N/A	N/A	N/A	\$40/\$20	\$40/\$20	\$10
Visit Number	Pre- Visit	Visit 1	Visit 2	Visit 3	Visit 4	Visit 5	Visit 6	Visit 7	Visit 8	Visit 9
Visit description	Initial Visit	Baseline	pre-quit	quit day	wk 1 post quit	wk2 post quit	wk4 post quit	wk12 post quit	wk26 post quit	wk52 post quit
IF GENOTYPE DATA IS NEEDED										
Blood Sample	X									
SSAND	X									
Realm-R	X									
Measurement of expired breath CO	X									
ASSESSMENTS										
Screening Questions at Baseline (before consent)		X								
Contact Information Form		X								
Baseline Assessment (Demographics/smoking status/Tobacco History/ Environmental History/ Brief Medical history)										
Brief WISDM37	X									
Measurement of expired breath CO	X							X**	X**	
WSWS	X	X*	X	X*	X*	X*	X*	X	X*	X*
Adverse Event Assessment	X	X*	X*	X*	X*	X*	X*	X		
Follow-up Assessment (smoking status, Timeline follow back, environmental factors)		X	X	X	X	X	X	X	X	X
Pill/Medicine Count								X		
Expectations								X		
Adherence self reported		X	X	X	X	X	X	X		
INTERVENTION COMPONENTS										
Approximate Counseling (minutes)	15	10	10	10	10	10	10	10		
Medication (cNRT, varenicline, placebo)	X	X	X	X	X	X	X			
Blood Sample- if pre-visit was not needed	X									

\*indicates a brief version of assessment; \*\*if self-reported abstinence CO data for biochemical confirmation

## ***E3 Initial Visit and Visit 1***

### Initial Visit (if needed)

Participants recruited from the community or volunteer for health will have a two hour initial visit to provide a blood sample for genetic analysis, and ask questions about health, use of alcohol and drugs, personality and family smoking history, and a carbon monoxide breath test.

The initial visit if needed for the genetic data will take approximately two hours and includes the following:

Blood sample  
Realm-R

---

Semi Structured Assessment of Nicotine Dependence – Short Version (SSAND)  
Alveolar CO level

Visit 1:

At the next visit (visit 1), participants will receive a baseline assessment of smoking history and withdrawal symptoms. This visit will take approximately 90 minutes.

The baseline assessment includes the following:

Demographics  
Smoking history  
Medical history  
Environmental factors  
Beck Depression Inventory (BDI)  
Beck Anxiety Inventory (BAI)  
Alveolar CO level  
Contact Information Sheet  
Adverse Events Screener  
Brief WISDM 37  
WSWS

They will receive baseline cessation counseling, being randomized to nicotine or placebo patches or varenicline or placebo along an instruction sheet, and set a quit date.

#### **E4 Visit 2-9**

At Follow up visits at the last day pre-quit, quit date, 1 week, 2 weeks, 4 weeks, 3 months, 6 months, and 1 year after the quit date, administer follow up assessments.

At follow up visits, all participants will receive the follow up visit assessment.

The follow up assessment by phone includes the following:

Smoking Status  
Non-study treatment data  
Patch/Lozenge/Pill use and potential side effects  
Adherence  
Medical History  
Environmental factors  
Adverse Events Screener  
WSWS

At the in-office follow up visits at 12 weeks and 6 months post-quit, the subject will provide a breath sample for alveolar CO level.

In follow visits up to 12 weeks after quit date, subjects receive smoking cessation counseling. This session will be the final counseling session.

#### **4.a Safety and Compliance Monitoring**

This study has a Data Safety and Monitoring Plan (DSMP), and a Data and Safety Monitoring Board (DSMB).

The Individual Patient Safety Committee (IPSC) will include the study's key personnel: [name]., M.P.H., Sc.D., a psychiatrist; [name]., a psychologist; [name]., a psychiatrist; The IPSC will review monthly reports on all participants. The IPSC will be blinded to the patient's group assignment.

In addition, we have a Data Safety and Monitoring Board (DSMB). The DSMB specifies overall monitoring that will be conducted by the principal investigator, including timely reporting of AEs and SAEs. Every 6 months, the DSMB will convene to review the overall safety data, and data on safety summarized by treatment condition. As per NIH guidelines, the objective of these reviews will be to determine whether continued conduct of the trial poses any undue risk for participants.

The DSMB will include 1) a board-certified psychiatrist, [name], 2) a cardiologist, [name], 3) an internist specialize in critical care and pulmonary health, [name], 4) an internist with expertise in stroke prevention and personalized antithrombotic therapy, [name], and 5) a statistician with expertise in research methodology, especially multicenter clinical trials and analysis of administrative data sets, [name]. All five have extensive experience with clinical trials. The DSMB will be blinded through the trial and convene every 6 months to compare the groups with respect to adverse events, dropouts, withdrawals, suicidality, and other problems as well as efficacy. They will make a recommendation at each meeting regarding whether to continue or discontinue the trial, the decision will be adjudicated by the Washington University Human Studies Committee.

#### **4.b Medical Monitoring**

The principal investigator will be responsible for routine monitoring of the trial's progress. This monitoring includes scheduled biweekly meetings with study staff and review of written documentation. Data that are reviewed at these meetings include the number and type of participants enrolled, the number and reasons for exclusions from enrollment, the number of participants treated and the stage of intervention, a summary and an individual review of any unanticipated health events, and outcome data. In addition, any unanticipated health events that raise concerns (e.g., allergic reaction, symptoms suggestive of nicotine toxicity) will be immediately reported to the study physicians (PI psychiatrist).

To facilitate participant safety, study participants must meet study inclusion and exclusion criteria. Once enrolled, follow-up protocols will assess the presence of medication side effects and unanticipated health events at all study visits and follow-up contacts. We will recommend dosage/use alterations as per good clinical practice if the patient experiences symptoms of nicotine toxicity or other troublesome side effects. We will refer patients to the study physician as needed.

If participants are smoking regularly, we will tell them to continue taking the study medication and set another quit date as soon as possible. Should either excessive risk to study participants and/or lack of measurable benefit to study participants be determined, the study will be stopped and all participants notified in a manner appropriate to the nature of the risk and/or lack of benefit.

---

This DSMP requires that investigators notify the Washington University IRB in a timely manner of the occurrence of any unanticipated health events which are severe, unanticipated, and possibly related to study medication or protocol. If the unanticipated health event might be related to the medication use, both the Food and Drug Administration (FDA) and the manufacturer (Glaxo, Inc. or Pfizer, Inc.) will be notified within 5 days of investigators becoming aware of the event. Examples of a serious unanticipated health event would be untoward occurrences that result in death, are life-threatening, require hospitalization or prolonging of existing hospitalization, create persistent or significant disability/incapacity, or involve congenital anomaly/birth defects. Unanticipated health events would include less serious problems that merit reporting because they are severe, unanticipated, and possibly related to study participation. Any serious unanticipated health event will be queried and reported even if it appears that the serious unanticipated health event is unrelated to study participation. The principal investigator will also be responsible for the accurate documentation, investigation, and follow-up of all study-related unanticipated health events.

Unanticipated health event assessment, recording, reporting and investigation will be accomplished through staff training, structure/standardized assessments of untoward occurrences/events, and regular monitoring by study physicians and other study investigators. The principal investigator has ultimate responsibility for ensuring that unanticipated health events are detected and reported.

#### **4.c Definitions of Adverse Events**

Adverse events are assessed in each follow up visit up to the end of treatment.

With respect to the pharmacotherapy, participants will be made aware of the common side effects before they consent to participate in the study. It should be noted that the nicotine patch is available over the counter. The nicotine patch has very few side effects, but participants may have a local skin reaction, and rarely, individuals may have a more systematic allergic reaction. The most common side-effects associated with the nicotine patch are diarrhea, indigestion, nausea and vomiting, dry mouth, muscle and joint pain, sleeplessness, and abnormal dreams. Side effects associated with wearing an adhesive patch include skin rash, redness, and itching or irritation of the skin. In most cases, these side effects have been mild to moderate in intensity and go away once the patch is removed. Although most smokers have tolerance to nicotine, symptoms of acute nicotine toxicity (nausea and vomiting) are possible.

#### **4.d Classification of Events**

With respect to the pharmacotherapy, participants will be made aware of the common side effects before they consent to participate in the study. It should be noted that the nicotine patch is available over the counter. The nicotine patch has very few side effects, but participants may have a local skin reaction, and rarely, individuals may have a more systematic allergic reaction. The most common side-effects associated with the nicotine patch are diarrhea, indigestion, nausea and vomiting, dry mouth, muscle and joint pain, sleeplessness, and abnormal dreams. Side effects associated with wearing an adhesive patch include skin rash, redness, and itching or irritation of the skin. In most cases, these side effects have been mild to moderate in intensity and go away once the patch is removed. Although most smokers have tolerance to nicotine, symptoms of acute nicotine toxicity (nausea and vomiting) are possible.

#### **4.e Data Collection Procedures for Adverse Events**

Adverse events are assessed in each follow up visit up to 1 year.

#### **4.f Reporting Procedures**

This DSMP requires that investigators notify the Washington University IRB in a timely manner of the occurrence of any unanticipated health events which are severe, unanticipated, and possibly related to study medication or protocol. If the unanticipated health event might be related to the medication use, both the Food and Drug Administration (FDA) and the manufacturer (Glaxo, Inc. or Pfizer, Inc.) will be notified within 5 days of investigators becoming aware of the event. Examples of a serious unanticipated health event would be untoward occurrences that result in death, are life-threatening, require hospitalization or prolonging of existing hospitalization, create persistent or significant disability/incapacity, or involve congenital anomaly/birth defects. Unanticipated health events would include less serious problems that merit reporting because they are severe, unanticipated, and possibly related to study participation. Any serious unanticipated health event will be queried and reported even if it appears that the serious unanticipated health even is unrelated to study participation. The principal investigator will also be responsible for the accurate documentation, investigation, and follow-up of all study-related unanticipated health events.

Unanticipated health event assessment, recording, reporting and investigation will be accomplished through staff training, structure/standardized assessments of untoward occurrences/events, and regular monitoring by study physicians and other study investigators. The principal investigator has ultimate responsibility for ensuring that unanticipated health events are detected and reported.

#### **4.g Adverse Event Reporting Period**

Adverse events will be recorded and reported throughout the entire duration of this study follow up period of 1 year for each participant.

#### **4.h Post-study Adverse Event**

Post-study adverse events will be recorded when the subject volunteers to report such events to the investigator team.

### ***E5 Study Outcome Measurements and Ascertainment***

**Smoking Status and Withdrawal:** All subjects will be contacted via phone for assessments of smoking status. We will assess long term outcomes following the SRNT Workgroup recommendations (Hughes et al, 2003).

Primary Outcome Measure:

7-day point prevalence abstinence [Time Frame: Week 12]

The definition of this measure requires: (a) no self-reported smoking (not even a puff of a cigarette) for at least the 7 days prior to the assessment, and (b) CO biochemical verification of abstinence.

**Secondary Outcome Measures:**

Continuous Abstinence (11 weeks) [Time Frame: 12 weeks with the first 1 week initial grace period]

The definition of this measure requires: Not taking even 1 cigarette puff from target quit date to end of treatment with the first 1 week initial grace period.

7-day point prevalence quit rate [Time Frame: Week 24]

The definition of this measure requires: (a) no self-reported smoking (not even a puff of a cigarette) for at least the 7 days prior to the assessment, and (b) biochemical verification of abstinence.

Number of days to lapse and relapse [Time Frame: Assessed from the target quit day through 52 weeks.]

The number of days to lapse is defined as the number of days from the target quit date until the participant reports smoking (even a single puff). The number of days to relapse is defined as the number of days from the target quit day until the first of seven consecutive days of smoking.

Initial Cessation [Time Frame: Assessed for the first seven days after the target quit date.]  
Defined as at least 1 day of abstinence during the first 7 days after the target quit day.

A research assistant will be ascertaining smoking status. Finally, we will gather carbon monoxide (CO) data at 12-wk in-person visits to biochemically validate self-reports: CO>8ppm will indicate smoking.

**Other Assessments:** WSWS, Environmental factors will be assessed in each follow up visits.

## **F Statistical Plan**

### ***F1 Sample Size Determination and Power***

We will recruit 822 subjects for this study to examine whether genotypes predict the efficacy and side effects of cessation medications. The sample size is based on the statistical power calculation based on current research findings. Based on published finding of effect size (OR=3.1), we will have power of 0.84 to detect a hypothesized interaction effect size of 2.0 with the study design (2 sided  $\alpha=0.05$ , abstinence rate 20% in the placebo group).

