### **2.d Randomization Method and Blinding**

The participants will be randomized with the ratio 1:1:1 to the treatment arm of combination NRT (nicotine patch and lozenge) plus smoking cessation counseling, or the treatment arm of varenicline plus smoking cessation counseling, or the treatment arm of placebo (patch and lozenge or pill) plus smoking cessation counseling.

Participants will be randomly assigned to 1) combination NRT plus counseling, 2) varenicline plus counseling, or 3) placebo plus counseling. SAS Version 9 statistical software will be used to generate the random assignment table stratified by CHRNA5 genotype rs16969968. The group assignment and genotype will be coded to ensure that the double blind is maintained, and the interface will prevent staff from having access to the participant's assignment and genotype until after the baseline and post treatment assessments have been completed.

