### **3.b Treatment Regimen**

During the baseline visit (visit 1), all participants will be randomized at 1:1:1 to 1) one arm of combination nicotine and smoking cessation counseling, or 2) varenicline and smoking cessation counseling, and 3) another arm of placebo and smoking cessation counseling at no cost to participants. Participants will receive enough patches to last 12 weeks. The duration of medication treatment is 12 weeks (standard for participants who smoke >9 cigs/day=8 weeks of 21mg, 2 weeks of 14mg, and 2 weeks of 7mg nicotine patches; standard for participants who smoke 5-9 cigs/day=8 weeks of 14mg and 4 weeks of 7mg;).

**Nicotine Lozenge:** The 4 mg dosage is recommended for patients who take their first cigarette within 30 minutes of waking and the 2mg dosage is recommended for patients who take their first cigarette more than 30 minutes after waking. Participants will begin taking lozenges a week before abstinence to replace some cigarettes. Participants will then take 1 lozenge every 1-2 hours for 6 weeks, then 1 lozenge every 2-4 hours for 3 weeks, and 1 lozenge for every 4-8 hours for 3 weeks. Participants will be encouraged to take a minimum of 4 pieces/day unless this amount produces adverse effects.

**Varenicline:** Varenicline will be initiated with a titration for 7 days before the quit date. Before the quit date, participants will take one 0.5mg tablet daily for 3 days, then two 0.5mg tablets for 4 days (one in the morning and one in the evening). After the quit date (day 8), participants will take 1mg tablet in the morning and in the evening.

**Placebo:** 50% of participants assigned to the placebo group will receive placebo patch/lozenge, and 50% will receive the placebo pill as a control for the two active medication arms.

All participants will be given complete instructions on proper medication use, and will be urged to contact his/her physician and a study hotline number immediately in case of listed symptoms of nicotine toxicity or side effects. Dose changes or discontinuation of NRT may be recommended; all changes will be addressed in analyses of adherence outcomes.

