### ***F3 Analysis Plan***

All analyses will first be conducted separately for European Ancestry (EA) and African American (AA) due to distinctly different allele frequencies and linkage disequilibrium across ancestry. If consistent genetic effects are seen across ancestry, samples of EA and AA ancestry will be combined in analyses with the covariate of race.

---

We will compare the abstinence outcome in the two placebo groups (placebo nicotine patch plus placebo nicotine lozenge vs. placebo varenicline pill). If they are comparable which is consistent with prior experience of other placebo-controlled smoking cessation trials, they will be pooled for further analyses.

The primary outcome is CO-confirmed point prevalent abstinence at end of treatment (12 weeks), defined if subjects deny smoking during 7 days prior of the end of treatment and provide a breath sample with CO <8 ppm.

Hypothesis #1 is to examine whether medication effect (cNRT vs. placebo) varies with CHRNA5 (i.e. a genotype X medication interaction). A series of generalized linear models will be used to examine main effects of genotype (rs16969968) and medication before testing genotype x medication interactions, with sex, age, and study cohort as covariates using logistic regression models.

Hypothesis #2 is to examine whether medication effect (varenicline vs. placebo) varies with CHRNA5 (i.e. a genotype X medication interaction). A series of generalized regression models will be used to examine main effects of genotype (rs16969968) and medication before testing genotype x medication interactions, with sex, age, and study cohort as covariates using logistic regression models.

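### F1's power of 0.84 for an interaction effect of 2.0 is not reached by either primary hypothesis at 274 vs 274: read as an odds ratio with Hardy-Weinberg genotypes, the maximum is about 0.71 (per-allele) or 0.45 (two-group)

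*Combined protocol and SAP*

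**What the plan says.** Section F1 begins "We will recruit 822 subjects for this study" and then states that "we will have power of 0.84 to detect a hypothesized interaction effect size of 2.0 with the study design". It gives two-sided alpha 0.05, 20% abstinence on placebo and a published OR of 3.1. It does not give the n per comparison, the genotype coding, the allele or genotype frequencies, the medication effect, or how 3.1 relates to 2.0.

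Section 2.d sets the allocation: "The participants will be randomized with the ratio 1:1:1 to the treatment arm of combination NRT", with varenicline and placebo as the other two arms. Section F3 defines two separate interaction tests in logistic regression: "Hypothesis #1 is to examine whether medication effect (cNRT vs. placebo) varies with CHRNA5" and "Hypothesis #2 is to examine whether medication effect (varenicline vs. placebo) varies with CHRNA5".

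Two further provisions affect n. Section 3.b splits the placebo arm: "50% of participants assigned to the placebo group will receive placebo patch/lozenge, and 50% will receive the placebo pill". F3 pools the two placebo forms conditionally: "If they are comparable which is consistent with prior experience of other placebo-controlled smoking cessation trials, they will be pooled for further analyses". F3 also states: "All analyses will first be conducted separately for European Ancestry (EA) and African American (AA) due to distinctly different allele frequencies". The ancestry groups are combined afterwards if the genetic effects are consistent.

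**The concern.** 822 divided by three is 274 per arm, so each hypothesis rests on at most 274 vs 274, two thirds of the 822. Tests of interaction on a binary outcome are demanding, and 0.84 for an odds ratio of 2.0 looks too high for that n.

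This is the only power statement in the available text for the two hypotheses the trial is built on, and F1 says the sample size rests on it. A reader who trusts 0.84 will take a null interaction as fairly strong evidence against a pharmacogenetic effect of that size. If the true power is far lower, that inference is not justified.

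**Working it through.** **Inputs from the documents.** N = 822 at 1:1:1, so n = 274 per arm; interaction effect 2.0; two-sided alpha 0.05 (z = 1.96); placebo abstinence 20%; logistic model with a genotype-by-medication term.

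**Assumptions, because F1 is silent.** The 2.0 is an odds ratio. Genotypes are in Hardy-Weinberg proportions. Coding is per-allele (0/1/2) or two-group (0/1). Allele frequency and main effects are varied.

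**Method.** The model is logit(p) = a + b_g·G + b_t·T + b_i·G·T with b_i = ln 2 = 0.693. The variance of the interaction estimate is the sum of the two within-arm slope variances, each 1/(n·Σ w(G − Ḡ_w)²). Here w is the genotype share times p(1 − p), and Ḡ_w is the w-weighted mean of G. Power = Φ(0.693/SE − 1.96).

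**Worked case, per-allele, frequency 0.50, no main effects.**
- Placebo: p = 0.20 throughout and Var(G) = 0.5, so the variance is 1/(274 × 0.16 × 0.5) = 0.0456.
- Active: p = 0.200, 0.333, 0.500 for G = 0, 1, 2. The weighted sum of squares per subject is 0.1001, so the variance is 1/(274 × 0.1001) = 0.0364.
- SE = √0.0821 = 0.286; 0.693/0.286 = 2.42; power = Φ(0.46) = **0.68**.

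**Worked case, two groups of equal size, no main effects.**
- Placebo: 1/(274 × 0.16 × 0.25) = 0.0912.
- Active: 1/(137 × 0.16) + 1/(137 × 0.222) = 0.0785.
- SE = √0.1697 = 0.412; 0.693/0.412 = 1.68; power = Φ(−0.28) = **0.39**.

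**Maximum over all unstated inputs.** The search covered allele frequency 0.02–0.98, genotype OR 0.2–3 and medication OR 0.3–5, at 274 vs 274 and interaction OR 2.0.

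| Coding | 20% = overall placebo rate | 20% = rate in reference genotype |
|---|---|---|
| Per-allele | 0.706 | 0.709 |
| Two-group | 0.431 | 0.447 |
| Three-level, 2 df | 0.600 | not run |

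The per-allele maximum of 0.706 falls at frequency 0.53, genotype OR 0.73 and medication OR 1.99.

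**Power by allele frequency** (per-allele, genotype OR 0.7–1, medication OR 1–2):

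| Frequency | Power |
|---|---|
| 0.10 | 0.28–0.33 |
| 0.20 | 0.46–0.52 |
| 0.30 | 0.58–0.62 |
| 0.35 | 0.62–0.66 |
| 0.50 | 0.68–0.70 |

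Simulation (3000 trials per setting, no main effects) gave 0.30, 0.51, 0.61, 0.65 and 0.68 at these frequencies.

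**A bound that does not depend on abstinence rates or allele frequency.** p(1 − p) is at most 0.25, and Var(G) is at most 0.5 under Hardy-Weinberg. So SE ≥ √(2/(274 × 0.25 × 0.5)) = 0.242 and power ≤ Φ(0.693/0.242 − 1.96) = 0.82. For two groups Var(G) is at most 0.25 and the bound is 0.53. Even 50% abstinence in every cell would not give 0.84.

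**Smaller n.** If the placebo forms are not pooled (137 vs 274), the per-allele maximum is 0.51. In an ancestry stratum holding half the sample (assumed, 137 vs 137) it is 0.42.

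**Attempts to reproduce 0.84.** A two-arm split of all 822 (411 vs 411, per-allele, no main effects) gives 0.842 at frequency 0.50. Over the main effects tried, that split gives 0.82–0.85 at 0.40 and stays below 0.84 at 0.38 or less. Section E2 still describes randomisation to two groups, but the documents do not show how 0.84 was obtained, so this origin is only a possibility.

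**What 274 vs 274 can detect with power 0.84** (per-allele): an OR of about 2.3 at frequency 0.50, 2.4 at 0.35, and 2.8 to 3.0 at 0.20, depending on main effects.

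**The case against.** **Effect scale.** F1 does not call 2.0 an odds ratio, and a ratio of risk ratios could give 0.84. That is true. However, an OR stands in the same sentence, the model is logistic, and no other scale is mentioned.

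**Genotype distribution.** The ceiling depends on Hardy-Weinberg proportions. With 0/1/2 scores and shares of 36/28/36, power is 0.83–0.85; with 38/24/38 it is 0.84–0.87; with equal thirds, 0.80–0.82. The arithmetic is right, but the documents describe no such mix. The primary marker is a single SNP, and stratifying the randomisation by genotype balances the arms without enriching them. Pooling two ancestries half and half with different allele frequencies, as an illustration, gave only 0.57–0.70.

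**Reverse coding.** Scoring the other allele (interaction OR 0.5), with 20% placed in the reference genotype, genotype OR about 2 and medication OR about 4, gives 0.77 per-allele and 0.47 two-group. The 0.71 and 0.45 ceilings therefore apply to an interaction coded as 2.0. This variant is extreme and still falls short of 0.84.

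**Not a per-hypothesis claim.** F1 names neither hypothesis. Pooling both active arms (548 vs 274) gives about 0.80 per-allele, and at least one of the two tests being significant gives at most about 0.83. Neither is a stated primary hypothesis and neither reaches 0.84.

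**Contingencies.** F3 expects the placebo forms to be comparable and allows the ancestries to be combined. It does not say what follows if the placebo forms differ, so 137 vs 274 is an inference. The main result uses the full 274 vs 274 and does not depend on these steps.

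**Appendix K10.** F3 and F4 refer to a detailed SAP that appears here only as a heading. It might contain the missing inputs. F1 would still need to agree with it.

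**Conclusion.** The concern holds. With 2.0 as an odds ratio, Hardy-Weinberg genotypes, 20% placebo abstinence and 274 vs 274, each primary interaction test has power of at most about 0.71 (per-allele) or 0.43 to 0.45 (two-group). The chance of missing a true interaction of 2.0 is at least 29% or 55% per hypothesis, against the 16% that F1 implies. At an allele frequency of 0.20 to 0.35 with per-allele coding, power is roughly 0.46 to 0.66. The result assumes the odds-ratio scale and Hardy-Weinberg proportions. A different scale or an unusual genotype mix could yield 0.84, but the documents describe neither. The error lies in the stated power and leaves the tests themselves unaffected. It should be corrected because the sample size is justified by this figure.

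**What to change.** Delete 0.84 and restate F1 separately for the cNRT and varenicline hypotheses, giving:

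- n = 274 vs 274;
- that 2.0 is an odds ratio, and for which genotype contrast;
- the genotype coding of the primary test;
- the assumed genotype frequencies, overall and by ancestry;
- the assumed medication effect;
- the resulting power;
- the interaction OR detectable with power 0.84 (about 2.3 to 3.0 per allele for frequencies 0.50 to 0.20).

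If another effect measure or genotype mix produced 0.84, state it in F1 with its inputs. Make the SAP match.

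The cost is rewording only, with a less favourable stated power. Keeping 0.84 for an OR of 2.0 would instead require about 409, 448 or 631 per arm at frequency 0.50, 0.35 or 0.20 (per-allele, no main effects).
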